1.2 Secondary Objective

To determine if late functional outcomes are improved following the administration of autologous cells compared with subjects in the control group. Efficacy outcome measures:

- 1. aMRI volumetric white matter, grey matter, and CSF space volumes at Baseline, 1 year and 2 years post-treatment. Detailed volumetric analysis of the corpus callosum and white matter tract such as the corticospinal tract will be measured (fractional anisotropy and mean diffusivity) as well. Specific white matter tract analysis will be identified at baseline MRI and correlated with motor function studies as the primary lesion of interest. Total volumes and specific tract lesions will be analyzed and correlated with functional outcomes.
- 2. The following functional outcomes studies will be performed at baseline, 6 months, 1 year after infusion, and 2 year after infusion.
 - a. Gross Motor Function Measures
 - b. Psychological Assessment Batteries

2. BACKGROUND

2.1 Rationale for Initiating Protocol in Children

Cerebral palsy (CP) is a worldwide major health problem, caused by brain damage during pregnancy, delivery or the immediate postnatal period. According to the Centers for Disease Control (2011), cerebral palsy is the most common motor disability in childhood, affecting approximately 1 in 303 8-year-old children in the US. It is estimated that the average lifetime costs associated with cerebral palsy are approximately \$921,000 per person. There are no effective treatments for CP. Our stem cell research team in neurological disorders, in addition to other research centers, has shown that

various types of cell therapies are safe and may enhance recovery from brain injuries such as stroke and TBI. The mechanisms underlying how certain cell therapies exert beneficial effects are likely multi-factorial and include the ability to modulate the inflammatory response after brain injury and to release factors that stimulate intrinsic brain repair processes such as neurogenesis, angiogenesis, and synaptogenesis. In fact, stem cells may adapt the profile of different repair promoting factors they secrete depending on the timing, type, and chronicity of the brain injury.

2.2 Pre-Clinical Data

[figure not shown]
Cerebral Palsy and potential therapeutic time window: Stem cells and other types of cell therapies have been extensively studied in animal models of cerebral hypoxia-ischemia that simulate the conditions leading to cerebral palsy. Stem cells have been found in animal models of neonatal hypoxia to improve outcome when administered up to 10 days after injury and up to 30 days after stroke in young adult rats. One month in a rat would translate to several years in humans. Furthermore, one of the principal brain cell types that regulates inflammation after brain injury are microglia, which recent studies have shown remain activated for years after brain injury in patients (Ramlackhansingh, 2011). This chronic inflammatory response likely evolves over time and is associated with severe cognitive impairments. Our research has identified that some types of cell therapies target and modulate microglia to reduce ongoing damage after brain injury. Overall, these data raise the possibility that stem cells may carry therapeutic potential in children chronically disabled with cerebral palsy.

A large body of data indicates that both umbilical cord and bone marrow cells are attractive and highly promising sources of cell therapies for patients with brain injuries. The intravenous administration of mononuclear cells from umbilical cord and bone marrow has been shown in multiple animal models of cerebral ischemia to improve neurological outcome (Meier, 2006). A pilot study has already shown that autologous cord blood is safe to administer in infants with acquired neurological disorders (Sun, 2010). Pre-clinical and Phase 1 clinical studies have shown that BMMNC treatment for neurological injury reduces the neuro-inflammatory response and may preserve neural tissue. The precise mechanism of action and potential time-window of treatment has not been defined. Data in rodent models of stroke suggests that the 30-day time window may be the limit of potential effectiveness (de Vasconcelos dos Santos, 2010). In contrast, longitudinal imaging studies of patients after moderate TBI have shown progressive axonopathy, detectable by DTI in the regions of interest described above (callosal volumes, FA, MD) from the 2 week post-injury time point to 6 months postinjury (Kumar, 2009). This progressive, ongoing evolution of the imaging findings suggests progressive demyelination and gliosis (Kraus, 2007). Preservation of white matter volumes and callosal volumes correlate positively and significantly with neurocognitive outcome. Given the safety findings in our pediatric Phase 1 study, we have designed this study to use an imaging based/ structural outcome variable as our primary measure of efficacy.

3. STUDY DESIGN

This is a randomized, blinded, placebo-controlled, cross-over study designed to treat CP in pediatric subjects with an IV infusion of autologous bone marrow mononuclear cells or autologous umbilical cord blood cells. A total of 30 subjects (15/arm) will be enrolled into the study. Subjects will be randomized 2:1 (treatment: sham). All subjects will return for follow-up at 6 months, 12 months, and 24 months post-treatment. At the 12 months post-treatment visit, those subjects who originally received the sham will be offered the BMMNC or hUCB treatment (Figure 1).

Figure 1.

Thirty subjects will provide a preliminary assessment of potential SAEs with a 10 to 15% incidence that we would be able to detect with reasonable confidence. The sample size would also allow us to acquire point estimates of different events that we would use for a larger efficacy study. The sample size determination is based on the historical treatment effect size of 15% decrease in gray and white matter volumes. Preservation

of this volume is based on the Phase 1 pediatric acute treatment of severe TBI using autologous bone marrow derived mononuclear cells as compared to historical control volumetric analyses by Wilde et al. (Wilde, E, et. al. 2005; Cox, C et al., 2011.)

Drug/Biologic: A single dose of intravenously administered autologous BMMNC or hUCB. The BMMNC dose will be 6X10⁶ cells/kg body weight infused over 15 minutes at a 1 million cells/ml concentration. For the hUCB arm, the minimum acceptable dose will be 2X10⁶cells/kg body weight based on rodent data (Lu, 2001), and the maximum allowable dose will be 10X10⁶cells/kg. The target dose will be the maximum available dose within this range. The bone marrow harvest, the hUCB reanimation, cell processing and product infusion will occur at Children's Memorial Hermann Hospital and the Griffin Stem Cell Laboratory.

Placebo: 0.9% saline will be infused in an identical syringe over the same rate as if receiving a cell infusion, (See "Blinding of Placebo Infusion").

4. SELECTION AND ENROLLMENT OF SUBJECTS

4.1 Inclusion Criteria

- 1. Children with diagnosis of Cerebral Palsy (spastic CP due to periventricular white matter damage or neonatal brain injury from perinatal stroke or intraventricular hemorrhage)
- 2. Gross Motor Function Classification Score level II-V
- 3. Ages 24 months to 10 years
- 4. English speaking, if verbal
- 5. Ability to travel to Houston for treatment and follow-up

4.2 Exclusion Criteria

- 1. Known history of:
 - a. Intractable seizures
 - b. Traumatic brain injury
 - c. Genetic disorder (as demonstrated by newborn screening or genetic diagnostic testing)
 - d. Recently treated or current infection
 - e. Renal insufficiency or altered renal function (as defined by serum creatinine > 1.5 mg/dl at screening)
 - f. hepatic disease or altered liver function (as defined by SGPT > 150 U/L [non-contusion related], and/or T. Bilirubin >1.3 mg/dL at screening)
 - g. HIV+ (as demonstrated by positive blood test)
 - h. Immunosuppression (as defined by WBC <3,000 cells/ml at screening)
 - i. Infectious related neurological injury
 - j. Sensitivity to Ethylene Oxide (EtO) [found in fumigants and disinfectants]
- 2. If Athetoid CP diagnosis, other etiologies such as degenerative, mitochondrial, and metabolic disorders must be excluded, and the outcome assessments must be able to be conducted to assess for potential treatment effects

- 3. Normal brain MRI
- 4. Evidence of acute illness at the time of infusion, such as, but not limited to, fever (temperature > 37.5 C), vomiting, diarrhea, wheezing or crackles
- 5. Progressing neurological disease (as defined by Batten Disease, Leukodystrophies, Metabolic disorders, Mitochondrial disorders, Neurotransmitter disorders)
- 6. Microcephaly, macrocephaly, cortical malformations, genetic disorders of dysgenesis brain malformations due to infection or metabolic disorders
- 7. Pulmonary disease requiring ventilator support
- 8. If hUCB candidate, banked cord cells totaling <10 million/kg
- 9. If hUCB candidate, any positive maternal infectious disease test (Hepatitis A/B, HIV 1, HIV 2, HTLV 1, HTLV 2, and Syphilis), (refer to Appendix D)
- 10. If hUCB candidate, cord blood sample contamination
- 11. Participation in a concurrent interventional research study
- 12. Unwillingness to return for follow-up visits
- 13. Contraindications to brain MRI (metal implants, dental braces, etc.)
- 14. Any subject that the investigators, feel in their opinion the study intervention is unlikely to benefit the subject will be a screen failure
- 15. Previous participating in other stem cell treatment or research studies

5. STUDY INTERVENTIONS

5.1 Bone Marrow Arm

5.1.1 Subject Recruitment

Fifteen pediatric subjects without banked umbilical cord blood meeting eligibility criteria will be enrolled into the bone marrow arm of the study. The parent(s)/LAR of potential subjects will contact the research team at The University of Texas Health Science Center at Houston. During this telephone call, an overview of the study and basic eligibility requirements will be reviewed. If eligibility requirements are met and the parent(s)/LAR willing to participate, instructions will be provided on forwarding medical records to the research team for review and a consent and authorization for release of information (for contact with the subjects primary care provider [PCP]) will be sent to the parent(s)/LAR. After receipt of medical records and contact with the PCP (if indicated) a telephone conference call will be scheduled with the parent(s)/LAR. During the call, study procedures and the informed consent document will be reviewed. Time will be given to answer questions. The parent(s)/LAR will not be pressured to make a decision on participation during the call. Parent(s)/LAR choosing to participate in the study will be asked to return the signed informed consent in the postage paid envelope provided.

After receipt of the signed informed consent document, the parent(s)/LAR will be contacted by the research team to schedule the baseline/treatment visit. The parent(s)/LAR will be responsible for making all travel arrangements.

5.1.2 Randomization

The randomization sequence will be computer-generated. The subject will be assigned to the treatment or control arm in a 2:1 ratio using sequentially numbered, opaque, sealed envelopes prepared by a member of the Center for Surgical Trials and Evidence-based Practice (C-STEP) not involved in the clinical trial.

5.1.3 Baseline Visit and Bone Marrow (Placebo) Harvest/Infusion

The outpatient baseline visit will be conducted in the Pediatric Outpatient Surgery Clinic. At the baseline outpatient visit, the signed informed consent document will be reviewed with the parent(s)/LAR and assent obtained from the subjects if they are able to do so. During this 1 day outpatient visit, subjects will undergo baseline assessments including physical and neurological exams, laboratory tests, chest radiograph, oxygen saturation monitoring, psychological testing, and quality of life measurements. The neuroexam will be videotaped for blinded assessments of dystonia using standardized scales validated for use on children with CP. The research team will review information from the baseline assessments to ensure the subject remains eligible for participation and that there are no unanticipated reasons to exclude the subject, (such as recent infection). After completing the outpatient baseline visit assessments, eligible subjects will be admitted to a Children's Memorial Hermann Hospital pediatric unit.

The bone marrow harvest will be performed under sedation (Propofol) and local anesthetic before or immediately after the baseline DTMRI. The subject may be logrolled to a 45 degree angle for access to the posterior iliac crest or remain supine to access anterior iliac crest. The bone marrow harvest will be performed under aseptic conditions. The bone marrow harvest is performed using either an 11-gauge needle or 15-gauge needle inserted into the iliac crest(s). Approximately 2 – 3 mL (< 40 kg body weight) to 5 – 6 mL (> 40 kg body weight) of bone marrow aspirate will be obtained and transferred in as sterile manner in a validated Coleman® cooler at ambient temperature to the Griffin Stem Cell Laboratory (GSCL). An additional blood sample will be drawn for infectious disease testing that includes HIV 1 and II, Hepatitis B and C, HTLV 1 and II, Syphilis, CMV, West Nile Virus, and ABO blood type. Transportation, processing, assessing and quality assurance at GSCL are described in the Chemistry & Manufacturing section of the IND. Approximately 6 – 7 hours after bone marrow aspiration, subjects will receive the BMMNC via peripheral or central intravenous infusion in a time not to exceed 30 minutes. The product will be infused within 30 minutes of receipt at Children's Memorial Hermann Hospital, and will remain in the cooler until ready for infusion.

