5.1.4 Sham Harvest Procedure

A 3mL sample of peripheral blood will be collected immediately prior to the harvest sham procedure. The sham harvest will be performed under sedation (Propofol) with a local anesthetic used at the site. The subject may be log-rolled to a 45 degree angle for access to the posterior iliac crest or remain supine to access the anterior iliac crest. An 11-gauge or 15-gauge needle will be used to puncture through the skin, but will not be inserted into the iliac bone. The puncture site will then be steri-stripped closed and covered with an identical external bandage. No bone marrow aspiration or harvest will

take place. The clinical care providers will not be allowed to observe the harvest and will not be informed of the assigned group.

Approximately 6 – 7 hours after the sham bone marrow aspiration, subjects will receive a placebo saline infusion via peripheral or central intravenous infusion in a time not to exceed 30 minutes. Identical to the BMMNC infusion, the placebo will be infused within 30 minutes of receipt at Children's Memorial Hermann Hospital, and will remain in the cooler until ready for infusion.

- 5.1.5 Schedule of Vital Signs during Harvest & Infusion
 - 1. Immediately prior to bone marrow or sham harvest
 - 2. During harvest: vital signs continually monitored & recorded every 5 minutes
 - 3. Post-harvest: g 15 minutes x 4 (1st hour), g 30 minutes x 4 (next 2 hours), and then every hour until the infusion
 - 4. Immediately prior to infusion
 - 5. During infusion: vital signs continually monitored & recorded every 5 minutes
 - 6. Post Infusion: q 15 minutes x 4 (1st hour), q 30 minutes x 4 (next 2 hours), g 1 hour x 4 (next 4 hours), and then every 4 hours thereafter.

BMMNC Dosing 5.1.6

Our target dose is 6×10⁶ BMMNC/Kg body weight. The target dose is based on preclinical animal data where cells were administered locally (intramyocardial) in a clinical protocol for patients with congestive heart failure (cell harvest of > 30×10⁶ cells or approximately 0.4×10⁶ cells/Kg body weight from a total of 50 mL of bone marrow harvested) (Perin et al., 2003), and our pediatric Phase I clinical trial using a similar protocol (Cox et al., 2011). In other studies, rat BMMNCs were isolated and 2×106 cells/350gm were administered intravenously (Lu et al., 2001).

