GSCL estimated that over 1×10⁸ cells could be obtained from the proposed bone marrow harvest, and this was confirmed in our Phase I Trial. The cells will then be resuspended to a 1 mL/Kg final volume. Below is a sample dosing calculation:

70Kg subject at the dose target: Total Dose= Subject weight (Kg) X 6×10⁶ cells Dose required= $70\text{Kg X }6\times10^6 \text{ cells} = 420\times10^6$ Yield expected= 350 mL bone marrow to yield 7×108 cells or 700×106 cells.

Smaller harvest yields may necessitate reducing our dose target. If the yield is below the target, then the upper doses may be impractical and we will use/infuse the maximum obtainable dose for each subject. Data will be analyzed as such. It will not be a protocol deviation if the dose target is not reached.

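### The marrow harvest volume in section 5.1.3 contradicts the volume, yield and dose in section 5.1.6; a missing per-kg unit is the likely cause

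*Combined protocol and SAP*

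**What the plan says.** Section 5.1.3 (Baseline Visit and Bone Marrow (Placebo) Harvest/Infusion) gives the only operative instruction on how much marrow to take: "Approximately 2 – 3 mL (< 40 kg body weight) to 5 – 6 mL (> 40 kg body weight) of bone marrow aspirate". No per-kg unit is attached to either volume.

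Section 5.1.6 (BMMNC Dosing) then says four things that depend on that volume:

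- The dose: "Our target dose is 6×10⁶ BMMNC/Kg body weight". Section 3 gives the same figure.
- The expected yield: the cell laboratory estimated that over 1×10⁸ "cells could be obtained from the proposed bone marrow harvest, and this was confirmed in our Phase I Trial".
- A worked example for a 70 kg subject, needing 420×10⁶ cells: "Yield expected= 350 mL bone marrow to yield" 7×10⁸ cells.
- A shortfall clause: if the yield is too low, whatever dose can be obtained is infused, missing the target is not a protocol deviation, and "Data will be analyzed as such".

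Section 5.1.6 also cites a heart-failure protocol that collected more than 30×10⁶ cells "from a total of 50 mL of bone marrow harvested".

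**The concern.** The 70 kg subject in section 5.1.6 falls in the above-40-kg band of section 5.1.3, yet one section takes 350 mL and the other 5–6 mL. That comparison is volume against volume and needs no assumption about cell yield. The expected yield of over 1×10⁸ cells is also hard to square with a harvest of a few millilitres.

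The aspirate volume fixes the size of an invasive procedure in a sedated child, and it fixes the cell dose. An operator, an ethics board or the DSMB cannot tell from the protocol which procedure is meant. The primary objective is safety, and a safety conclusion needs a known exposure. Because a missed dose target is not a deviation, a harvest at the literal volume would not be flagged as a dosing problem.

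**Working it through.** **Inputs.** Harvest volumes from section 5.1.3: 2–3 mL below 40 kg, 5–6 mL above 40 kg. From section 5.1.6: target 6×10⁶ cells/kg; example of 70 kg, 350 mL and 7×10⁸ cells; expected yield over 1×10⁸ cells; reference harvest of more than 30×10⁶ cells from 50 mL. The documents give no body weights for the children. I assume 20 kg and show 10–39 kg, staying under the 40 kg cut.

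**1. The plan's own example.**
- Dose = 70 × 6×10⁶ = 420×10⁶ cells, as stated.
- Implied yield = 700×10⁶ / 350 mL = 2×10⁶ cells/mL.
- Implied harvest = 350 mL / 70 kg = 5 mL/kg.

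**2. Volume against volume at 70 kg.** 350/6 = 58 and 350/5 = 70. The example harvests 58 to 70 times what section 5.1.3 prints.

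**3. Yield needed to reach 1×10⁸ cells.**
- From 2–3 mL: 1×10⁸/3 to 1×10⁸/2 = 33–50×10⁶ cells/mL, or 17–25 times the example's 2×10⁶.
- From 5–6 mL: 1×10⁸/6 to 1×10⁸/5 = 17–20×10⁶ cells/mL, or 8–10 times.

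**4. Dose below 40 kg under three readings.** Percent of target = cells / (weight × 6×10⁶). Readings (a) and (c) use 2×10⁶ cells/mL and assume that yield scales linearly with volume.

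| Weight (assumed) | (a) 2–3 mL in total | (b) 1×10⁸ cells taken at face value | (c) 2–3 mL/kg |
|---|---|---|---|
| 10 kg | 6.7–10% | target met | 67–100% |
| 20 kg | 3.3–5.0% | at least 83% | 67–100% |
| 30 kg | 2.2–3.3% | at least 56% | 67–100% |
| 39 kg | 1.7–2.6% | at least 43% | 67–100% |

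At 20 kg the target is 20 × 6×10⁶ = 120×10⁶ cells.
- (a) 2–3 mL × 2×10⁶ = 4–6×10⁶ cells.
- (b) 100/120 = 83%. The full target is covered up to 1×10⁸ / 6×10⁶ = 16.7 kg.
- (c) 40–60 mL × 2×10⁶ = 80–120×10⁶ cells.

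**5. Does a per-kg unit reconcile the text?**
- 5 mL/kg × 70 kg = 350 mL, exactly the example.
- 3 mL/kg × 2×10⁶ = 6×10⁶ cells/kg, exactly the target.
- 1×10⁸ cells need 1×10⁸ / 2×10⁶ = 50 mL. That is reached at 50/3 = 17 kg (3 mL/kg) to 50/2 = 25 kg (2 mL/kg). Lighter children would fall short of 1×10⁸, so the fit is good but not complete.

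**6. Sensitivity to yield.** The reference harvest implies at least 30×10⁶/50 = 0.6×10⁶ cells/mL. At that figure a 20 kg child reaches 1.0–1.5% of target under (a), and 1.2–1.8×10⁶ cells/kg, or 20–30%, under (c). The percentages move a great deal. The 70 kg volume conflict does not move at all.

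**The case against.** The strongest objection is to the inferred cause. A weight step is natural for absolute volumes and odd for per-kg ones. With the unit added, and at 2×10⁶ cells/mL, children below 40 kg would yield 4–6×10⁶ cells/kg and larger subjects 10–12×10⁶ cells/kg, up to twice one constant per-kg target. The 350 mL line could be the faulty one instead. This stands as a reason to treat the missing unit as likely rather than established. It does not remove the conflict.

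Second, the 58- to 70-fold figure belongs to a 70 kg subject in a trial of children aged 24 months to 10 years. That is fair: the example is illustrative. It is still the protocol's own example, and the ambiguity below 40 kg remains.

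Third, every percentage of target under readings (a) and (c) rests on one back-calculated yield. That also stands, and step 6 shows how far the figures shift. A higher true yield would raise the dose under the literal reading, but it would not turn 5–6 mL into 350 mL.

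Fourth, section 5.1.6 already allows for low yields. That clause deals with shortfalls from a harvest. It does not choose between two incompatible harvest volumes.

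Finally, the unit might have been lost in reading the PDF. This cannot be excluded, since superscripts are lost nearby. But the sentence is otherwise intact, and per-kg units survive elsewhere, including in section 5.1.6. The IND is cited for transport, processing, assessment and quality assurance, not for aspirate volume.

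**Conclusion.** The concern holds. Sections 5.1.3 and 5.1.6 prescribe incompatible harvests: 5–6 mL against 350 mL for the same 70 kg subject, with no assumption needed. For a child assumed to weigh 20 kg, the literal and per-kg readings are 2–3 mL and 40–60 mL. In dose terms that is 3.3–5.0% against 67–100% of target, provided the example's 2×10⁶ cells/mL applies and scales linearly.

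A missing per-kg unit explains the text best but remains an inference. The literal reading is the extreme case, and nothing here shows that children receive too few cells. The matter is more than clerical because the figure governs an invasive procedure and sets the exposure on which the safety result will be judged.

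**What to change.** In section 5.1.3, state the intended aspirate volume with its unit (mL/kg if that was meant). Bring the expected yield and the worked example in section 5.1.6 into agreement with it, preferably using a weight plausible for the eligible ages. The sponsor must confirm which volume is right.

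Separately, give the clause on analysing the data as obtained some content: report delivered cells/kg for each child, and describe results by delivered dose rather than by the 6×10⁶/kg target. Section 9 specifies no dose-based summary at present.

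The cost is protocol wording, with no added patients, visits or procedures.

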5.2.3 Subject Recruitment

Fifteen pediatric subjects who have their umbilical cord blood banked with CBR and meet study criteria will be enrolled into the cord blood study arm. The parent(s)/LAR of potential subjects will contact CBR. After receiving permission to release the subject's contact information, CBR will then relay the contact information to the research team, who will then contact the parent(s). During this telephone call, an overview of the study and basic eligibility requirements will be reviewed. If eligibility requirements are met and the parent(s)/LAR willing to participate, instructions will be provided on forwarding medical records to the research team for review and a consent and authorization for release of information (for contact with the subjects primary care provider [PCP]) will be sent to the parent(s)/LAR. After receipt of medical records and contact with the PCP (if

indicated) a telephone conference call will be scheduled with the parent(s)/LAR. During the call, study procedures and the informed consent document will be reviewed. Time will be given to answer questions. The parent(s)/LAR will not be pressured to make a decision on participation during the call. Families choosing to participate in the study will be asked to return the signed informed consent in the postage paid envelope provided.

After receipt of the signed informed consent document, CBR will be notified to release cord blood information to the research team. The parent(s)/LAR will be contacted by the research team to schedule the baseline/treatment visit. The parent(s)/LAR will be responsible for making their travel arrangements.

Approximately 4 – 6 weeks prior to the scheduled procedure date, the subject will have the infectious disease testing for HIV 1 and II, Hepatitis B and C, HTLV 1 and II, Syphilis, CMV, and West Nile Virus. An additional 8 – 10 mL of blood will be collected at this time and shipped overnight to a Cell and Gene Therapy (CAGT) lab in Houston for HLA testing. All lab results will be sent to the research team for review prior to the baseline/treatment visit. If the subject has a positive HIV, Hepatitis B, or C test; they will be excluded from the study.

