5.2.6 Shipping of Cord Blood

For subjects randomized to receive hUCB at the baseline visit, the GSCL will request a segment of the subject's banked cord blood sample from CBR. The subject's HLA lab results will be compared to the cord blood sample for HLA type (6/6 match). Additionally, the cord blood segment will be tested for viability and cell count. Results from the HLA typing will be faxed to CBR to confirm the subject's identity. CBR will ship the frozen cord blood to the GSCL 7 – 14 days prior to the scheduled procedure, where it will be kept frozen until the morning of infusion. It is important to note that once cord blood has been shipped from CBR it cannot be returned. If the subject is randomized to the placebo group, cord blood unit will NOT be shipped. All HLA lab results will remain on record for reference at the 1 year cross-over visit (if indicated).

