8.5 Subject Replacement

Subjects will not be replaced once randomized.

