14. APPENDIX A

Bone Marrow Group:

												1
Study Procedures	Screening Period	Baseline Clinic Visit	Admission to MHH	Study Day 1 (Post-Infusion)	Study Day 2-21 (Post-Infusion)	* 6-Month Follow-Up Clinic Visit	* 1-Year Follow-Up Clinic Visit	* 1-Year Crossover Group Clinic Visit	Crossover Group Admission to MHH	Crossover Group Study Day 1 (Post-Infusion)	Crossover Group Study Days 2 - 21 (Post-Infusion)	* 2-Year End of Study Clinic Visit
Review of Medical Records	Х	х						х				
Consent		¹ X	9 3					Х				
Randomization		х									2	
History	Х	х				х	Х	Х				х
Physical		х	X	х		х	Х	Х	х	Х		х
Videotaped Motor/Cognitive Evaluation		х				х	х	х				х
Vital Signs		х	X	х	х	х	Х	Х	х	Х	Х	х
Infectious Disease Tests			² X									
Lab Evaluation		³ X	3X	3X	⁴ x	³ X	³ X	³ X	³ X	³ X	⁴ x	³ X
Chest X-Ray			х	х		х	Х		х	х		х
DT-MRI			Х				Х		Х		5	х
Bone Marrow / Sham Harvest			Х						⁶ x			
Stem Cell or Placebo Infusion			х						⁶ X			
Neuropsych Evaluation		х				×	x	x				х
Hospital Discharge				⁵ X						⁵ x		
Post-Infusion Safety Monitoring					х						х	
Evaluation for AE/SAEs		х	x	х	х	х	×	X	х	x	x	x

^{*} The 6 month return visit window is +/- 14 days from infusion and +/- 21 days for the 1 and 2 year return visits.

¹ The informed consent document will be sent to the family/LAR during the screening period and reviewed by conference call before the baseline visit.

². Infectious Disease Tests include HIV, Hepatitis, Syphilis, and West Nile Virus.

³ Lab tests include CBC with Differential and Platelets, and Comprehensive Metabolic/Coagulation Panels.

⁴ Post-infusion CBC and basic chemistry pannel on day 21 (+/- 7 days).

⁵ Subjects will receive 24 hours of monitoring post-infusion before discharge.

⁶. Placebo Crossover to BMMNC harvest and stem cell infusion.

Cord Blood Group:

Study Procedures	Screening Period	6 - 8 Weeks Before Visit	Baseline Clinic Visit	Admission to MHH	Study Day 1 (Post-Infusion)	Study Days 2 - 21 (Post-Infusion)	• 6-Month Follow-Up Clinic Visit	+ 1-Year Follow-Up Clinic Visit	* 1-Year Crossover Group Clinic Visit	Crossover Group Admission to MHH	Crossover Group Study Day 1 (Post-Infusion)	Crossover Group Study Days 2 - 21 (Post-Infusion)	* 2-Year End of Study Clinic Visit
Review of Medical Recods	х												
Consent			¹ x					Х	x				x
History			Х										8
Physical			х	Х	Х		Х	Х	Х	Х	Х		х
Infectious Disease and HLA Tests		²x							х				
CBR Release of Cord Blood Tests		³ X							х				
Randomization	1	⁴ x		6. F.									8

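### Some blood tests that define exclusions are scheduled after the steps they should gate: after randomisation and shipment of the unit in the cord arm (renal, hepatic, white-cell limits), and after randomisation, at the harvest admission, in the marrow arm (HIV)

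*Combined protocol and SAP*

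**What the plan says.** **Exclusions (4.2).** The renal item reads "Renal insufficiency or altered renal function (as defined by serum creatinine > 1.5 mg/dl at screening". The SGPT, total bilirubin and white-cell limits carry the same timing. A separate item reads "HIV+ (as demonstrated by positive blood test". All of these stand under one stem about known history.

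**Marrow arm.** In Appendix A the screening column has no laboratory evaluation. Randomisation and the first laboratory evaluation are both marked at the baseline clinic visit. The infection tests are marked only in the next column, hospital admission, with the footnote "Infectious Disease Tests include HIV, Hepatitis, Syphilis, and West Nile Virus". Section 5.1.3 describes that draw in the harvest paragraph ("An additional blood sample will be drawn for infectious disease testing that includes HIV 1 and II, Hepatitis B and C") and puts the infusion about 6–7 hours after aspiration. The same section has the team review the baseline results and admit only eligible children.

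**Cord arm.** Section 5.2.3 draws the child's infection panel 4–6 weeks before the procedure and states "If the subject has a positive HIV, Hepatitis B, or C test; they will be excluded from the study". Section 5.2.5 randomises after those results and the bank's cell data are in. The Appendix A footnote makes randomisation conditional on viable cells, HLA match and infection results, and does not mention the renal, hepatic or white-cell limits. The first laboratory evaluation is at the baseline visit. Section 5.2.6 ships a cell-assigned child's unit 7–14 days before the procedure and warns that "once cord blood has been shipped from CBR it cannot be returned".

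**Replacement (8.5).** "Subjects will not be replaced once randomized".

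**The concern.** An exclusion protects the child and the comparison only if its result is known before the step it should prevent. Here some results arrive later.

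In the cord arm, a child outside a renal, hepatic or white-cell limit can be randomised and, if assigned to cells, have the unit sent out of the bank before the trial measures that limit. In the marrow arm, a child whose HIV infection is not already known from the records can be randomised, sedated, and harvested or sham-harvested before the trial has its own HIV result.

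For the analysis, each such child is a randomised subject who should not have been entered and who is not replaced, in groups of about 10 and 5. Section 9 defines no analysis population and does not say how such a child is counted.

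**Working it through.** No stated power or sample-size figure is in dispute, so this is a check of sequence. The arithmetic only shows scale.

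**Step 1. Order of events, from 4.2, 5.1.3, 5.2.3–5.2.7 and Appendix A.**

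| Arm and test | When 4.2 applies it | When it is scheduled | Steps already taken by then |
|---|---|---|---|
| Cord: creatinine, SGPT, bilirubin, white cells | at screening | baseline visit | randomisation; shipment if assigned to cells |
| Cord: child's infection panel | – | weeks before the visit | none; correctly placed |
| Marrow: HIV | no timing given | hospital admission, with harvest | randomisation; no hold on harvest or infusion |
| Marrow: creatinine, SGPT, bilirubin, white cells | at screening | baseline visit | not determinable: same visit as randomisation, no order stated |

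**Step 2. Which safeguard catches which failure.** The eligibility review at the end of the baseline visit comes before admission in both arms.
- Marrow lab limits: the review should stop a failure before harvest.
- Cord lab limits: the review can stop the infusion, but cannot undo randomisation or shipment.
- Marrow HIV: the review cannot act on a sample that has not yet been drawn.

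**Step 3. Group sizes.** Section 3 gives 15 children per arm, randomised 2:1. If the ratio is met within each arm, that is 15 × 2/3 = 10 on cells and 15 × 1/3 = 5 on sham. One unreplaced loss is 1/10 = 10% of a cell group or 1/5 = 20% of a sham group. About 10 cord units ship before the recipient's first study measurement of the four limits.

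**Step 4. Effect of one loss on the safety aim.** Section 3 aims at serious events with 10–15% incidence. The chance of seeing at least one is 1 − (1 − p)^n.

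| Children on cells | p = 10% | p = 15% |
|---|---|---|
| 10 (one arm) | 1 − 0.90^10 = 65.1% | 1 − 0.85^10 = 80.3% |
| 9 | 61.3% | 76.8% |
| 20 (both arms) | 87.8% | 96.1% |
| 19 | 86.5% | 95.4% |

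**Step 5. How often.** The documents give no rate. As an assumption, let 1% to 5% of cord-arm children fail a lab limit that was not known beforehand.
- At least one among 15 randomised: 1 − 0.99^15 = 14% to 1 − 0.95^15 = 54%.
- At least one among 10 shipped units: 1 − 0.99^10 = 10% to 1 − 0.95^10 = 40%.

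This range should not be carried to the marrow arm, where the only established route is an HIV result not already known.

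**The case against.** The strongest reply is that the exclusions stand under a known-history stem, and medical records are reviewed at screening, with contact to the primary care provider if indicated. A documented HIV infection or renal disease would exclude a child at that point. The harvest-day panel may also serve product quality and labelling rather than eligibility: 5.1.9 mentions blood for quality assurance and infection testing, and Appendix D says donor testing is not required for autologous use. A release rule could sit in the manufacturing section of the IND, which is not part of these documents.

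Much of this stands, and it limits the point to children whose result is not already known. It does not remove it. The protocol does not require recent results in the records, and numeric limits tied to screening imply a measurement then. A product-release rule could hold an infusion, but would not come before randomisation.

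A reader might also infer the following, which the documents do not support:

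- *That ineligible children are in fact being randomised, harvested or shipped for.* The schedule allows it; nothing shows how often it happens.
- *That the marrow lab limits come after randomisation, or that such a failure reaches harvest.* The two share one visit with no stated order, and the review precedes admission.
- *That cord-arm labs follow randomisation by 6–8 weeks.* The Appendix A column with that label also holds shipment, dated 7–14 days before the visit, and 5.2.3 places the infection draw 4–6 weeks ahead. The order is clear; the interval is not.
- *That a shipped unit is lost.* It stays frozen at the processing laboratory. What is lost is the option of returning it to the bank.
- *That the hepatitis B/C wording, found only in the cord section, biases cells against sham.* Randomisation is within each arm, so it does not.

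**Conclusion.** The point holds in a limited form and should be fixed; it does not undermine the trial. In the cord arm, the four laboratory limits are first measured after randomisation and, for about 10 children, after a shipment that cannot be reversed. In the marrow arm, the trial's own HIV test follows randomisation and takes place at the harvest admission, with nothing holding harvest or infusion for the result. No turnaround time is given. Even a result back before the infusion would come after randomisation and normally after harvest.

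Each late exclusion could cost 10% of a cell group or 20% of a sham group. It is a possible rather than certain loss, because 8.3 and 8.4 ask withdrawn children to continue evaluations. The statistical effect of one case is small: about 4 percentage points on detecting a 10% event in one cell group, and 1.3 points with both cell groups combined. The case for change rests more on avoiding a needless sedated procedure or shipment, and on how little the correction costs.

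The conclusion assumes that 2:1 is met within each arm and that no unseen document imposes an earlier check. The frequency of late exclusions is unknown.

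**What to change.** 1. **Cord arm.** Add a CBC, creatinine, ALT (SGPT) and bilirubin to the blood already drawn 4–6 weeks ahead under 5.2.3. Require results against the 4.2 limits before randomisation and before shipment.
2. **Marrow arm.** Move the infection panel to a draw before the baseline visit. Have the results that bear on eligibility in hand before the envelope is opened, and open it only after the baseline labs have been reviewed.
3. **Appendix A.** Show these draws in pre-randomisation columns of both schedules, and keep the baseline labs as a safety re-check.
4. **Infection criteria.** Reconcile 4.2, 5.1.3 and 5.2.3 on which infection results in the child exclude in each arm. The hepatitis B/C exclusion on the child's own test appears only in the cord section, although the marrow arm draws the same tests. Which rule applies is for the investigators to settle; the sections need to agree.

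The cost is a protocol amendment, one earlier local draw for marrow-arm families (a moved test rather than a new one), a few extra tubes at an existing cord-arm draw, and modest laboratory expense.
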